#### 3. Collaborative Research

a) If any non-UCB institutions or individuals are engaged in the research, explain their human research roles and what human subjects training they have/PI has planned to provide.

This study will involve the following collaborating institutions. All Nicaraguan institutions are part of the Nicaraguan Ministry of Health and fall under IRB review conducted by the CNDR/MOH (see Section 3b):

Centro de Salud Sócrates Flores Vivas (HCSFV), Managua, is a Ministry of Health health center that serves as the primary site for the pediatric dengue cohort study and provides healthcare to the study participants. At the Health Center [name], a licensed physician and head of the Health Center, will be responsible for overseeing participant care.

Protocol # 2010-09-2245 Date Printed: 10/05/2018

**Protocol Title:** Pediatric Cohort Study of Dengue Transmission in Nicaragua

Biomedical Non-Exempt Protocol Type:

Date Submitted: Draft Approval Period: Draft

This Print View may not reflect all comments and contingencies for approval. Please check the comments section of the online protocol. Important Note:

Questions that appear to not have been answered may not have been required for this

submission. Please see the system application for more details.

Center, will be responsible for overseeing participant care.

Hospital Infantil Manuel de Jesus Rivera (HIMJR), Managua, is the national pediatric reference hospital. It is the best-equipped pediatric facility in the country. All cases of severe dengue in the greater metropolitan area of Managua are referred to the HIMJR. All suspected dengue cases from the cohort presenting with signs of alarm are referred to study physicians at the HIMJR.

National Virology Laboratory, Centro Nacional de Diagnóstico y Referencia, Ministry of Health, Managua, performs all serological and virological tests for dengue diagnosis and will process the samples collected as part of this study. [name] is the Head of the National Virology Laboratory and the Major Foreign Collaborator (Foreign Prinicipal Investigator) of the site. [name] is responsible for the study site in Nicaragua.

The Sustainable Sciences Institute (SSI) oversees the conduction of the study at the three institution mentioned above. SSI is a non-profit organization that has an agreement with the Nicaraguan Ministry of Health to administer collaborative research projects such as this study. SSI relies on the Nicaraguan Ministry of Health's IRB approval, as registered in the OHRP database (FWA00009658).

[name] is an Assistant Professor in the Department of Epidemiology, University of Michigan, Ann Arbor. [name] will analyze data generated by the study and contribute to design study instruments (e.g. questionnaires). [name] specializes in the epidemiologic features of infectious diseases in tropical regions. She has been working with the Nicaraguan Ministry of Health and [name] for the past 10 years. She has completed CITI online human subjects training, and the NIH human subjects course. [name] has taught a responsible conduct of research course, meeting NIH requirements, at UC Berkeley.

The following institutions are collaborating on investigations that do NOT involve human subjects research, but rather analysis of coded samples withOUT personal identifiers in order to meet the scientific objectives of the grants/study.

[name] at McMaster University in Canada has extensive experience in host genetic studies, and has just finished one contract with NIH examining host susceptibility or resistance to West Nile virus infection. We will collaborate with [name] and a network he has put together in the Americas as well as Asia to examine host genetic contributions to severe disease as well as protection against dengue virus as part of a dengue host genetics contract from NIH that was recently awarded.

[name], [name] at the Colorado State University (CSU) is an expert in the field of RNA Virology. She will use the metabolomics platform at CSU to identify new biomarkers for dengue diagnosis and prognosis. This analysis will be performed using serum as well as non invasive samples such as urine and saliva.

[name] at the Icahn School of Medicine at Mount Sinai in New York is recognized for her studies on the mechanisms that regulate the development and function of innate myeloid cells including dendritic cells and macrophages. [name], also at the Icahn School of Medicine at Mount Sinai, is an expert in the identification of T cell epitopes and the mapping of T cell responses to specific antigens. Together, they will characterize immune signatures in dengue virus infections, including innate immune response and competence and T cell and dendritic cell function.

[name] at the Icahn School of Medicine at Mount Sinai in New York has published extensively on and pioneered research in integrating diverse types of large scale, high dimensional data to construct system-level, predictive models of complex phenotypes like common human diseases. [name], also at

Protocol # 2010-09-2245 Date Printed: 10/05/2018

Protocol Title: Pediatric Cohort Study of Dengue Transmission in Nicaragua

Protocol Type: Biomedical Non-Exempt

Date Submitted: Draft Approval Period: Draft

Important Note: This Print View may not reflect all comments and contingencies for approval. Please check

the comments section of the online protocol.

Questions that appear to not have been answered may not have been required for this

submission. Please see the system application for more details.

-

the Icahn School of Medicine at Mount Sinai is an expert in Bioinformatics. Together they will coordinate data analysis generated by various collaborators of the Dengue Human Immunology Project Consortium (DHIPC) and develop models to identify signatures that define immune response and categories/fingerprints/profiles that correlate with infection outcome.

[name] at the Icahn School of Medicine at Mount Sinai in New York is an expert in large-scale biology and application of systems biology to biomedical research. His group will be in charge of data management and dissemination from/to collaborators of the Dengue Human Immunology Project Consortium (DHIPC).

[name] leads a laboratory focusing on systems and quantitative immunology at the National Institute of Allergy and Infectious Diseases (NIAID), National Institutes of Health (NIH). He also co-directs the Trans-NIH Center for Human Immunology (CHI) and leads its research program in systems human immunology. In relation to analysis of selected samples from the Nicaraguan cohort study, he will supervise the bioinformatic processing of the RNASeq or microarray gene expression data obtained. He will lead the design of and contribute substantially to the statistical analyses and quantitative modeling to investigate the effects of age, gender, and age-dependent and age-independent inter- vs. intra-individual variation in gene expression and immune profile in the study population. He will have access to limited metadata, as prepared by study data managers using un-linkable codes and de-identified data, and selected pre-collected de-identified specimens collected in PAXgene solution.

[name] is a Senior Research Scientist at Stanford University. The primary focus of his research has been to explore the use of the transcriptome as a tool for understanding the epidemiology of infectious disease and the biological basis for the variation in clinical outcomes. [name] will contribute to the overall study design and will work on functional and statistical analysis of processed RNAseq data from selected participants of the Nicaraguan cohort study to investigate the effects of age, gender, and individual variation in gene expression and immune profile in the study population. He will also coordinate efforts with [name] and researchers in Nicaragua to optimize subject and sample selection and associated metadata to generate hypotheses for future studies. He will have access to limited metadata, as prepared by study data managers using un-linkable codes and de-identified data, and selected precollected de-identified specimens collected in PAXgene solution.

b) If any non-UCB institutions or individuals are collaborating in the research, complete the table below and attach any relevant IRB approvals in the Attachments section.

Non-UCB institutions

Protocol # 2010-09-2245 Date Printed: 10/05/2018

Protocol Title: Pediatric Cohort Study of Dengue Transmission in Nicaragua

Protocol Type: Biomedical Non-Exempt

Date Submitted: Draft
Approval Period: Draft

Important Note: This Print View may not reflect all comments and contingencies for approval. Please check

**Protocol Type:** Biomedical Non-Exempt

Date Submitted: Draft **Approval Period:** Draft

This Print View may not reflect all comments and contingencies for approval. Please check the comments section of the online protocol. Questions that appear to not have been answered may not have been required for this submission. Please see the system application for more details. **Important Note:** 

Protocol # 2010-09-2245 Date Printed: 10/05/2018

**Protocol Title:** Pediatric Cohort Study of Dengue Transmission in Nicaragua

Biomedical Non-Exempt Protocol Type:

Date Submitted: Draft Approval Period: Draft

This Print View may not reflect all comments and contingencies for approval. Please check the comments section of the online protocol. Important Note:

Questions that appear to not have been answered may not have been required for this

submission. Please see the system application for more details.

\* \* \* Subject Population \* \* \*

## 5. Subject Population

Describe proposed subject population, stating age range, gender, race, ethnicity, language and literacy.

All participants will live in District II, Managua, Nicaragua, the catchment area for the Health Center Socrates Flores Vivas (HCSFV). No discrimination will take place in terms of race or gender; however, the age of study participants will be limited to children ages 2 to 17 years old as children have the highest burden of dengue. The subjects may be of three vulnerable populations: the illiterate, the poor, and children.

b) State the maximum number of subjects planned for the study. This number should account for all subjects to be recruited, including those who may drop out or be found ineligible. Explain how number of subjects needed to answer the research question was determined.

Since the beginning of the study in 2004 there have been a total 9,138 study participants. The current cohort size is 3,806 participants aged 2-14 years. The study maintains ~200-300 children in each 1-year age group from 2-14 years. Approximately 300 participants between 15 and 17 years of age will be included in the cohort this year due the age expansion, however these participants have been part of the cohort in the past and therefore do not increase the overall study participant number.

To maintain the cohort age structure and adjust for participants who age out of the cohort study, we plan to enroll up to 320 2-year old annually. Moreover, based on our study data from August 2004 to June 2010, we anticipate an annual loss to follow-up of ~6%. Thus, to maintain the cohort size and compensate for loss to follow-up, we plan to enroll up to 300 children aged 3 to 14.

We estimate that this sample size should yield 270-1155 infections per year, assuming an annual incidence of DENV infection of 7-30% (based on prior observed annual incidence rates in this and neighboring districts in Managua since 2001). Estimating that 10-20% of the infections will be symptomatic; this would result in 27-231 symptomatic dengue cases. Of these, ~15% (4-35 children) would require hospitalization for dengue, although we expect 2- to 3-fold more hospitalizations due to other diseases with similar clinical presentations. This cohort size ensures that even in years of relatively low transmission, a minimum number of symptomatic cases will be obtained.

The project period of our extended IRIDA/NIH funds (titled Epidemiological, Clinical & Immunological Studies of Zika, dengue and chikungunya, Grant Number: 5R01Al099631-07) is from 06/28/2012 to 05/31/2022. Hence, we plan to continue enrolling ~620 participants annually (up to 320 2-year old to maintain the cohort age structure and up to 300 participants aged 3 to 14 to compensate loss to follow-up) for ~5 years (2018-2022), thus increasing study sample size from 10,600 to 12,200. Further, NIH approval has been received to use the funds for an extended cohort, now incl. children 15 to 17 yrs of age (see attachments in section 22 of the protocol).

If any proposed subjects are children/minors, prisoners, pregnant women, those with physical or cognitive c) impairments, or others who are considered vulnerable to coercion or undue influence, state rationale for their involvement.

Protocol # 2010-09-2245 Date Printed: 10/05/2018

Protocol Title: Pediatric Cohort Study of Dengue Transmission in Nicaragua

Protocol Type: Biomedical Non-Exempt

Date Submitted: Draft
Approval Period: Draft

Important Note: This Print View may not reflect all comments and contingencies for approval. Please check

the comments section of the online protocol.

Questions that appear to not have been answered may not have been required for this

submission. Please see the system application for more details.

-----

The subjects may be of three vulnerable populations: the illiterate, the poor, and children. This study consists entirely of children, as children bear the greatest burden of dengue in Nicaragua. The purpose of this study is to maintain a pediatric cohort to determine the transmission of the disease and its clinical manifestations so therefore the population must be children. This study will also include the poor and illiterate as they represent a part of the general population in Managua and have a high burden of dengue disease.

#### 6. Recruitment

a) Explain how, where, when, and by whom prospective subjects will be identified/selected and approached for study participation. If researcher is subject's instructor, physician, or job supervisor, or if vulnerable subject groups will be recruited, explain what precautions will be taken to minimize potential coercion or undue influence to participate. See CPHS Guidelines on Recruitment for more information.

Due to the changes made to the letter of consent and the age extension up to 17 years of age, the whole cohort will be re-consented before starting the next annual 2019 sampling. The age extension will be offered to all 14 year old children who are participating in the study at the moment and the children who participated in the study before but who were retired in 2018 because they turned 15 years old. These reconsents and extensions will be offered upon visits to the health center or by household visits. Note that 15 years olds who actively withdrew from the study will not be contacted for re-enrollment, consistent with the protocol and the original consent form to which they agreed.

Following rationale will be presented when re-contacting former participants (those who have aged-out at age 15 years old) to participants/parents as to why they are being re-contacted and re-invited to participate in the study up to 17 years, which is consistent with the parent permission and assent forms: Based on the ongoing study it seems as if dengue, Zika and chikungunya affect older children more than younger children. We would like to determine whether that is true and understand why in order to improve medical care for children in the future.

New participants will be enrolled mainly during the annual sampling between February and April of each year and if necessary throughout the year to maintain the age structure of the cohort. Recruitment of new children will occur annually through house-to-house visits in the CSSFV service area or in the CSSFV through promotion of the study to the parents of 2-year-old who attend the Health Center for medical consultation. Appropriately trained study staff will provide information to parents or guardians, one-on-one or in small groups and answer questions related to the study. The discussion will begin with a preliminary explanation of the study, and the consent letter will be reviewed and read aloud together, providing a more detailed explanation of all aspects of the study.

b) Describe any recruitment materials (e.g., letters, flyers, advertisements [note type of media/where posted], scripts for verbal recruitment, etc.) and letter of permission/cooperation from institutions, agencies or organizations where off-site subject recruitment will take place (e.g., another UC campus, clinic, school district). Attach these documents in Attachments section. Please see eProtocol Attachments Check List for Non-Exempt Applications for more information.

No recruitment materials are used.

c) Will anyone who will be recruiting or enrolling human subjects for this research receive compensation for

Protocol # 2010-09-2245 Date Printed: 10/05/2018

Protocol Title: Pediatric Cohort Study of Dengue Transmission in Nicaragua

Protocol Type: Biomedical Non-Exempt

Date Submitted: Draft
Approval Period: Draft

Important Note: This Print View may not reflect all comments and contingencies for approval. Please check

the comments section of the online protocol.

Questions that appear to not have been answered may not have been required for this

submission. Please see the system application for more details.

-----

each subject enrolled into this protocol? If yes, please identify the individual(s) and the amount of payment (per subject and total).

No, payment to all staff is done on a monthly basis and is not dependent on the number of individuals enrolled in the study.

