#### 1. Purpose

Provide a brief explanation of the proposed research, including specific study hypothesis, objectives, and rationale.

The overall aim of the project is to maintain a pediatric cohort in Nicaragua to characterize the natural history of dengue transmission and the range of clinical manifestations over time and to establish a potential trial site for antiviral therapies or a safe tetravalent dengue vaccine.

The specific aims of this project are to:

- A. Prospectively determine the age- and serotype-specific incidence of symptomatic and asymptomatic dengue virus infection in children at highest risk of primary or secondary infection.
- B. Characterize symptoms and disease spectrum and provide appropriate medical attention to all suspected symptomatic dengue cases within the study population.
- C. Isolate representative samples of circulating dengue viruses and maintain a biobank of viruses.
- D. Maintain a biobank of clinical specimens (serum/plasma, white blood cells, host DNA, urine and saliva) from symptomatic and asymptomatic infected persons linked to clinical information for use by collaborators.
- E. Guarantee good clinical and laboratory practices through rigorous quality control.

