Re-enrollment and extension for children from 15 to 17 years of age Dengue cases have decreased continually in the cohort. Recent statistical analyzes revealed a large force of infection in 1997-1999 and a gradual decline thereafter. A change in the rate of specific immunity to dengue virus (DENV) in children was also observed over time: in 2004, approx. 50% of children ≥5 years were DENV-positive, but in 2015, this level of seropositivity was only reached to children of 11 years. With respect to Zika it was found that Seroprevalence increased with age. Due to these new findings it is important to study dengue, chikungunya and Zika in older children. We therefore want to include children 15 to 17 years of age in the cohort study.

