#### **Annual Sample Collection**

Each year between February and April, a study nurse will make contact with the participant and parent to collect a sample of blood from each participant. This contact will either occur at the health center or during a visit to the participant's home. If the drawn blood volume will depend on the age of the child. If the child is between 2 and 14 years of age a 8 ml blood sample will be collected at this time. If the child is 15 years of age or older a 14 ml blood sample will be drawn. The nurse will also ask questions about the participant's health, including whether the participant has been ill, has attended the HCSFV, or has traveled out of Managua. The entire appointment will last from 20 minutes to an hour depending on the number of children who are present. The total time commitment for the study will range between 1-3 hours per year, which will range widely depending on participant-driven medical visits and associated symptoms.

Within at least a week but no later than a month of the participant's annual sample collection, study participants will be expected to attend the HCSFV to (a) receive results from the Complete Blood Count (CBC) test performed on the blood sample, (b) make and receive a photo ID card, if the participant does not already have one, (c) scan the participant's fingerprint to facilitate future registration and identification, if such a scan is not already on file. A physician will be available to explain the laboratory results and make a follow-up appointment if necessary. This process generally takes 15 minutes or less per child.

Continuous Procedures over the Duration of the Study

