#### Other contact from the study and HCSFV

To evaluate compliance with the study procedure of early presentation to the HCSFV when ill and to promote Health Center attendance, study nurses will visit the houses of study participants. A full-scale undertaking where over 80% of houses are visited will occur at least once per year to evaluate participant compliance and satisfaction. At these visits, a brief questionnaire will be administered regarding the child's health and attendance to the HCSFV over the previous several months.

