X Assent/Permis Dengue\_permission\_Part\_D\_E sion Document xpand\_Edad\_Eng\_v1.0

Explain how, where, when, and by whom the permission of the parent or legal guardian of the child will be obtained.

Protocol # 2010-09-2245 Date Printed: 10/05/2018

**Protocol Title:** Pediatric Cohort Study of Dengue Transmission in Nicaragua

Biomedical Non-Exempt Protocol Type:

Date Submitted: **Draft** Approval Period: Draft

This Print View may not reflect all comments and contingencies for approval. Please check the comments section of the online protocol. **Important Note:** 

Questions that appear to not have been answered may not have been required for this

submission. Please see the system application for more details.

\_\_\_\_\_\_

This consent form Part D will be used to (i) expand the study age of current 14 year old participants to 17 years of age and (ii) re-consent participants who have reached 15 years of age in 2018 to join the cohort again until they are 17 year of age.

Study personnel will explain why we are expanding the study time or re-consenting and information regarding the general study will be provided to the adult(s) and children living in the same household, either one-on-one or in small groups.

The informed consent processes will involve reading the consent document (see attachment) aloud and the document, written in Spanish, will be presented to the potential participant. The interviewer will also sign the consent form as a witness/study representative. An unsigned copy of the consent form will serve as an information sheet describing the study procedures, risks, benefits, and contact information. Those who are not able to write will be asked to sign their name with their fingerprint. Some subjects may belong to lower socio-economic classes. As there are no financial incentives associated with this study, we do not think that this study involves any coercion; therefore, we do not feel we are putting this population at greater risk. Training for informed consent will include details on only obtaining assent and guardian consent from the appropriate person.

Only participants and children whose parents have consented to their participation and children over age 6 who have given assent will be permitted to expand or re-enter the study. Verbal assent will be obtained from all children aged 6 and older following parental consent. Informed guardian consent will be obtained from the appropriate person for participants under 18 years of age.

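### The re-contact rationale presents the age hypothesis to the 15-year-olds and their parents as an apparent finding, which could tilt attendance-based comparisons toward it

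*Protocol*

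**What the plan says.** Section 6 a) introduces the script: "Following rationale will be presented when re-contacting former participants (those who have aged-out at age 15 years old) to participants/parents". The rationale then reads "Based on the ongoing study it seems as if dengue, Zika and chikungunya affect older children more than younger children", followed by "We would like to determine whether that is true and understand why in order to improve medical care for children in the future". The protocol adds that this agrees with the permission and assent forms.

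Part D of the consent process covers those who turned 15 in 2018 and also current 14-year-olds. For both, section 20 says: "Study personnel will explain why we are expanding the study time or re-consenting and information regarding the general study will be provided". For the Part D permission form, this information goes to adults and children of the household.

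The evidence for the extension is in section 2: dengue cases have fallen, 50% dengue seropositivity is now reached only at a later age, and "With respect to Zika it was found that Seroprevalence increased with age".

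Aim A in section 1 is to "Prospectively determine the age- and serotype-specific incidence of symptomatic and asymptomatic dengue virus infection". Section 9 takes a blood sample from every participant once a year. Illness, by contrast, is recorded when the family comes to the health center. In describing the time commitment, section 9 refers to medical care "which will range widely depending on participant-driven medical visits and associated symptoms". House visits to more than 80% of homes at least yearly serve this purpose: "To evaluate compliance with the study procedure of early presentation to the HCSFV when ill and to promote Health Center attendance".

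**The concern.** The people in whom the age hypothesis will be tested are told beforehand that it seems to hold. The protocol describes no such statement to families with only younger children.

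An infected child who is never brought in while ill can be picked up only by annual serology, and would then look asymptomatic. If the statement makes parents of adolescents quicker to attend for a mild fever, some infections move from asymptomatic to symptomatic in that group. The shift favours the hypothesis. It would affect symptomatic incidence, the symptomatic share of infections and the clinical spectrum by age.

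The statement also outruns the evidence shown. The Zika result concerns infection, not illness. The dengue result shows that first infection now comes later, not that older children have more illness. Nothing is reported for chikungunya.

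**Working it through.** **1. The protocol's own yield (section 5 b).** Yield = N × annual incidence (7-30%) × symptomatic share (10-20%).
- N = 3,850: 3,850 × 0.07 = 269.5 and 3,850 × 0.30 = 1,155 infections; 269.5 × 0.10 = 27 and 1,155 × 0.20 = 231 symptomatic cases. These match the stated 270-1155 and 27-231.
- N = 3,806 (the stated cohort aged 2-14): 266-1,142 infections and 27-228 symptomatic cases, close to the stated figures.
- N = 3,806 + 300 = 4,106: 287-1,232 infections, which does not match. The stated yield is therefore for ages 2-14.

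**2. The 15-17 group.** About 300 participants, assuming the same rates apply to them: 300 × 0.07 × 0.10 = 2.1 to 300 × 0.30 × 0.20 = 18 symptomatic cases a year.

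**3. Bias with no true age difference.** Inputs: about 15% of symptomatic cases are hospitalised (section 5 b). Assumed: these attend regardless, and attendance for the other 85% rises by a relative amount r in the older group only. Rate ratio = 0.15 + 0.85 × (1 + r).
- r = 0: 1.00
- r = 0.10: 0.15 + 0.935 = 1.085, about 1.09
- r = 0.30: 0.15 + 1.105 = 1.255, about 1.26

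Applied to 2.1-18 cases a year, this is 2.1 × 0.085 = 0.2 to 18 × 0.255 = 4.6 extra cases. The symptomatic share changes by the same ratio, because the number of infections does not change.

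**4. Ceiling.** A rise r is possible only if baseline attendance is at most 1/(1 + r): 91% for r = 0.10 and 77% for r = 0.30. The protocol gives no baseline.

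**5. What it could do to a test.** Assume overall capture of 95% in the older group and 80% in the younger (ratio 0.95/0.80 = 1.19), with no true difference. The simulation used 200,000 Poisson draws, 300 against 3,806 children, and a Wald test on the log rate ratio with z > 1.96. Across the protocol's range of incidence and symptomatic share, a false finding of more illness in older children occurred in 6-12% of single years and in 9-28% of four-year periods. With 80% capture in both groups it occurred in about 3-4%.

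**6. Infection incidence.** If infection is ascertained from the annual sample, attendance does not enter, and the ratio stays at 1.00. That the sample serves this purpose is inferred from Aim A; the section on annual sampling does not say so.

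**The case against.** The script contains no request to attend. It is hedged, says the study wants to find out whether the impression is true, and explains honestly why the family is being contacted again. Nothing in the protocol shows that such a sentence changes care-seeking. Attendance is already promoted at all ages: willingness to use the health center is an entry condition, house visits are not limited by age, and physicians are available around the clock. The script also cites the ongoing study, whose data may hold more than section 2 reports. These points stand; they make the effect uncertain and perhaps small. They do not justify telling one age group the hypothesis when neutral wording would serve.

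A reader might infer more than the documents support:
- **That the whole older-versus-younger comparison is biased.** The annual sample is taken whether or not the child attended, so only attendance-based measures are exposed.
- **That only the 15-17 group hears the message.** The script is specified for those who aged out at 15. Current 14-year-olds receive a Part D explanation, and parents of adolescents also decide for younger siblings. The Part D forms and the revised consent letter are not among the documents at hand, so what other families are told is unknown.
- **That the house visits prove attendance varies.** They show only that compliance is evaluated and attendance promoted.
- **That the bias could never be examined afterwards.** The house-visit questionnaire covers health and attendance and would allow a check by age, although none is described.

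**Conclusion.** The point holds for attendance-based measures. The protocol fixes a statement that discloses the age hypothesis, as an apparent finding, to families in the group being tested, and section 2 does not support it for illness or for chikungunya. This creates an avoidable risk of differential ascertainment in the direction of the hypothesis.

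The size is not known. The ratio of 1.09-1.26 rests on three assumptions: a 10-30% rise in attendance for non-hospitalised illness, full attendance of the hospitalised 15%, and no effect in younger children. Spill-over to siblings would bring it nearer to 1.0, and if attendance does not respond there is no bias. A ratio of 1.1-1.3 would require the rise to apply to hospitalised cases as well, which is implausible. With only about 2-18 symptomatic cases a year in this group, a few extra attendances would still matter. The change is worth making before re-contact begins, since the statement cannot be taken back once families have heard it.

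**What to change.** - **Reword.** Replace the sentence in section 6 a), and any matching sentence in the Part D permission and assent forms, with neutral and truthful wording, for example: *We are extending the study to age 17 to learn how dengue, Zika and chikungunya affect children of different ages.* This still tells families why they are being contacted.
- **Same wording for all ages.** The whole cohort is to be re-consented before the 2019 sampling, so this needs no extra contact.
- **Check attendance by age.** Compare the attendance data already collected at the house visits between age groups.
- **Report both comparisons.** Show infection incidence by age from the annual samples beside symptomatic incidence by age. An excess seen only in the symptomatic measure could then be read with differential attendance in mind.

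Cost: a small rewording of the script and forms, with whatever ethics review that requires, and a little more analysis. No added visits, samples or staff.
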